1.1 Sample size calculation

A sample size of 28 was calculated in R version 4.2.2 using WebPower to provide a statistical power of 80%. The cutoff effect size was defined as the difference of 20 mmol in urine sodium measurement with an SD of 19, as described in a similar study design. Normal distribution, no cross-over effect, and sphericity were assumed for this calculation.

1.2 Planned recruitment rate and sample size correction

The recruitment process is estimated to be associated with a retention rate (participants recruited and completed the study follow-up, and assessed with valid primary outcome data) of 70%. Therefore, we aim to recruit 42 patients in total.

1.3 Statistical analysis plan

Descriptive analysis and statistical tests will be performed using the R software and Stata software. Data with a normal distribution will be presented as mean \pm SD and data with a skewed distribution will be presented as median \pm interquartile ranges (IQRs).

To balance the study for carryover effects, 6 subgroups of patients are needed to represent the 6 possible sequences of treatments. Generalized linear mixed models will be deployed to evaluate the differences among the effects of 3 different diuretic regimens (“treatments”). The treatments will be administered in a cross-over open-label trial (see section 8, “Trial design”), where each patient will receive every treatment exactly once with washout periods among the treatments. The sequence in which each patient will receive the 3 treatments will be randomized by a custom-made python script and determined a priori to balance for patients’ sex and HF type (i.e., male, female, HFrEF, HFpEF). Sequences will be designed using pairs of orthogonal Latin squares to balance for carryover effects (6 sequences in total). The dependent variables will be sodium weight (calculated as spot sodium concentration multiplied by the total volume of urine) and congestion score, with treatment type as an independent variable. To account for the crossover design effect, possible interactions between time (period of treatment) and intervention will be tested and the model will be adjusted for potential effects of the sequences of treatments, and the identity of the preceding treatment. To elucidate the differences between the 3 treatments, Tukey post-hoc testing and an adjustment for repeated measures will be performed whenever significant findings are observed. A value of $P < 0.05$ will be considered significant.

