1.4 Interim Analysis

An interim analysis is planned after recruiting and completing the follow up of 22 patients. This is in order to assess the power of the study.

Three options exist:

- 1) Statistical significance is achieved- then the study recruitment may stop and full analysis will be pursued.
- 2) No statistical significance achieved and study is futile or one of the study interventions is causing severe side effects and the study should be stopped at once (recruitment and treatments).
- 3) The results are not significant- an additional power analysis calculation will be reassessed based on the realistic 1st endpoint data accumulated.

Using the O'brein & Fleming method it is estimated that one additional patient should be recruited to keep the study powered.

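### Is Tukey after a significant overall test needlessly strict for comparing three diuretic regimens?

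*SAP*

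**What the plan says.** SAP section 1.3 sets up the comparison of the regimens: "Generalized linear mixed models will be deployed to evaluate the differences among the effects of 3 different diuretic regimens". The model allows for the crossover, in that "the model will be adjusted for potential effects of the sequences of treatments, and the identity of the preceding treatment". Pairwise comparison is conditional: "Tukey post-hoc testing and an adjustment for repeated measures will be performed whenever significant findings are observed". The level is a single one: "A value of $P < 0.05$ will be considered significant". The dependent variables are sodium weight and a congestion score.

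Section 1.1 gives the planning basis: "A sample size of 28 was calculated in R version 4.2.2 using WebPower to provide a statistical power of 80" (per cent), with "The cutoff effect size was defined as the difference of 20 mmol in urine sodium measurement with an SD of 19" and "Normal distribution, no cross-over effect, and sphericity were assumed for this calculation". Section 1.4 adds a look at the data: "An interim analysis is planned after recruiting and completing the follow up of 22 patients".

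The SAP does not name the test that acts as the gate, the within-patient covariance structure, or the exact meaning of the adjustment for repeated measures. The natural reading is that the gate is the overall treatment test for the outcome being modelled.

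**The concern.** Tukey's procedure controls the family-wise error for all pairs without any prior test. Placing it behind a significant overall test therefore looks like two corrections for one problem.

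Three treatments are also a special case. If any two of the three pairwise hypotheses are true, all three means are equal. A closed test then needs only the overall test and the single pairs: after a significant 5% overall test, each pair may be tested at 5% and the family-wise level stays at 5%.

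The pairwise contrasts show which regimen produces more natriuresis, and only 28 evaluable patients are planned. If power were being given away at no benefit, a change of wording would recover it.

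**Working it through.** **Inputs.** From the SAP: N = 28, power 80%, difference 20 mmol, SD 19, sphericity (1.1); three treatments, P < 0.05, gate then Tukey (1.3). Assumed: means 0/0/20 or 0/10/20, complete normal data, the unequal-SD patterns below, and how SD 19 enters the calculation, since the SAP does not say whether it belongs to a value or to a difference.

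**1. The plan's own figure.** Take f as the sample SD of (0, 0, 20) divided by 19: 11.547/19 = 0.6077. Then λ = n·f² = 28 × 0.3693 = 10.34, with 2 and 2(28 − 1) = 54 df. The noncentral F gives a power of 0.806 at n = 28, so the stated 28 is reproduced. Under this convention the implied error SD is 19·√2 = 26.87, because the exact noncentrality is n·Σ(deviation²)/σ² = 28 × 266.7/722 = 10.34. Steps 3 and 4 use this SD, so that the overall test has the plan's power.

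**2. Level used for each pair.** The Tukey cut-off for three means on 54 df, expressed as a t value, is 2.410, a pair-level two-sided α of 0.0194. With pair-specific standard errors on 27 df it is 2.479, or 0.0197. The closed test would use 0.05 after the gate.

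**3. Family-wise error under sphericity** (simulation, n = 28, no period or carryover terms).

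| Procedure | all means equal | one regimen far away |
|---|---|---|
| Gated Tukey, pooled error | 4.5% | 2.0% |
| Closed test, unstructured covariance | 5.0% | 5.0% |

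The planned procedure keeps the 5% level. The alternative uses the level more fully.

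**4. Power at the plan's 80%.**

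| Means | Pair | Gated Tukey, pooled | Closed, unstructured |
|---|---|---|---|
| 0/0/20 | each true pair | 64% | 70% |
| 0/10/20 | adjacent | 16% | 25% |
| 0/10/20 | extreme | 62.9% | 63.2% |

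The gate itself costs little. Ungated pooled Tukey gives 16.3% for adjacent pairs and 64.5% for the extreme pair, so adding the gate takes away less than 0.1 point and about 1.5 points. The difference between the columns therefore comes from Tukey and the choice of covariance, and hardly from correcting twice.

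**5. Unequal SDs: the gain can reverse.** If the regimen that differs has the small SD (30/30/10, means 0/0/20), power per true pair rises from 73% to 89%. If it has the large SD, or the middle regimen has the small one, power falls:

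| SDs | Means | Pair | Gated Tukey, pooled | Closed, unstructured |
|---|---|---|---|---|
| 12/12/25 | 0/0/20 | each true pair | 94.9% | 92.1% |
| 10/10/30 | 0/0/20 | each true pair | 89.7% | 82.3% |
| 25/12/25 | 0/10/20 | extreme | 80.4% | 70.2% |

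The losses are 2.8, 7.4 and 10.2 points. In the third case the adjacent pairs gain (24% to 42%). Part of each loss is the price of pair-specific standard errors.

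**6. What the alternative needs.** Unadjusted pairs keep 5% only if every component test is valid. With pooled errors after the gate, family-wise error is about 9% for SDs 25/25/12 and 10% for 30/30/10 (means 0/0/20). In the model with period and preceding-treatment terms these are 7.7% and 8.0%. With unstructured covariance but large-sample cut-offs, error is 6.0 to 6.6%. The gate must also be the overall test of that same outcome; Tukey tolerates a looser gate, unadjusted pairs do not.

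**The case for a change.** The strongest case for change is that the closed test is exact theory for three treatments and costs no patients. In the model with period, sequence and preceding-treatment terms, the gains can be substantial. With SD 19 as the within-patient SD and means 0/0/20, detecting both true pairs rises from 77% to 86%; with SD 27.07, from 36% to 48%. Against Tukey behind the same unstructured gate, no pair loses power under sphericity. The covariance structure and the adjustment for repeated measures are left open, and pooled errors are not safe for Tukey either: gated Tukey reached 5.5 to 6.7% with strongly unequal variances when all means are equal, and 8.1% in an extreme case with one regimen far away.

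The closure argument and the gains in those settings stand. So does the observation that the gate, the covariance and the adjustment could be described more fully. That is missing detail, however, and does not make Tukey the wrong choice. The non-sphericity figures concern pooled standard errors; dropping Tukey does not repair them, and in the same extreme case unadjusted pooled pairs reach 14.3%. The alternative also weakens protection for a true-null pair while two outcomes and an interim look already share the 5% level, and its error control has not been shown for the congestion score.

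**Conclusion.** The concern does not hold. Tukey after a significant overall test is a valid, mildly conservative procedure: 4.5% family-wise error when all regimens are equal and about 2% when one differs, with 28 patients under the sphericity assumed in section 1.1. Compared with the closed test, its cost at the plan's 80% power is about 6 points per true pair for means 0/0/20, about 9 points for adjacent pairs at 0/10/20, and practically nothing for the extreme pair. In return the plan keeps simultaneous intervals that match its tests, and a procedure that does not depend on the exact form of the gate. With some unequal-SD patterns pooled-error Tukey is the more powerful of the two, by 3 to 10 points. Statisticians may reasonably prefer either approach, and nothing in section 1.3 is stated wrongly or contradicted on this point.

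The conclusion rests on complete normal data, on reading the gate as the overall treatment test of the same outcome, and on either near-sphericity or pair-specific standard errors. The figures at 80% power also rest on the effect-size convention that reproduces the stated 28, and they leave out period and carryover terms.

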1.4 Interim Analysis

An interim analysis is planned after recruiting and completing the follow up of 22 patients. This is in order to assess the power of the study.

Three options exist:

- 1) Statistical significance is achieved- then the study recruitment may stop and full analysis will be pursued.
- 2) No statistical significance achieved and study is futile or one of the study interventions is causing severe side effects and the study should be stopped at once (recruitment and treatments).
- 3) The results are not significant- an additional power analysis calculation will be reassessed based on the realistic 1st endpoint data accumulated.

Using the O'brein & Fleming method it is estimated that one additional patient should be recruited to keep the study powered.

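### The efficacy stop at 22 completers is not tied to the O'Brien-Fleming method the SAP names; read literally, type I error is about 7.3–7.5% instead of 5%

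*SAP*

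**What the plan says.** - **Interim look.** SAP section 1.4: "An interim analysis is planned after recruiting and completing the follow up of 22 patients". The stated purpose is power: "This is in order to assess the power of the study".
- **Efficacy stop.** Option 1 of the same section: "Statistical significance is achieved- then the study recruitment may stop and full analysis will be pursued". It gives no level or boundary.
- **Significance level.** The only one in the SAP closes section 1.3: "A value of $P < 0.05$ will be considered significant". It does not separate an interim test from a final one.
- **Group-sequential method.** It appears once, at the end of section 1.4: "Using the O'brein & Fleming method it is estimated that one additional patient should be recruited to keep the study powered". It is not linked to option 1 or to the final test.
- **Continuation.** Option 3: "The results are not significant- an additional power analysis calculation will be reassessed based on the realistic 1st endpoint data accumulated". The final number of completers can therefore change after the look.
- **Base sample size.** Section 1.1: "A sample size of 28 was calculated in R version 4.2.2 using WebPower to provide a statistical power of 80"%.

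**The concern.** Section 1.4 makes the interim a formal efficacy look, because a positive result may end recruitment. Two tests of the same hypothesis, each at 0.05, have a combined false-positive rate above 0.05. The method the SAP names prevents this by setting a stricter level at each look, but the SAP uses it only to adjust the sample size.

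As a result, the text supports two rules. Following option 1 with the level in section 1.3, an analyst could stop at an interim P of 0.04. Following O'Brien-Fleming, the analyst could not. The final test is affected too: section 1.3 sets it at 0.05, whereas the named method needs a slightly lower level. The trial is open-label, so a threshold chosen after the interim P is known would be hard to defend.

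**Working it through.** **Inputs.** Interim at 22 completers, one extra patient, method O'Brien-Fleming (section 1.4); base size 28 with 80% power (section 1.1); retention 70% and 42 to be recruited (section 1.2); level 0.05 (section 1.3). Assumptions: two-sided testing, since the SAP does not state sidedness, and a final N of 28 + 1 = 29 completers. The second is consistent with section 1.2: 29/0.70 = 41.4, rounded up to 42.

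**Step 1. Reproduce the plan's extra patient.** The O'Brien-Fleming boundaries for two looks are z₁ = c/√t and z₂ = c, where t is the information fraction and c is set so that the total two-sided error is 0.05. At t = 22/28 = 0.786, the sample size inflation for 80% power is 1.0199. Then 28 × 1.0199 = 28.56, rounded up to 29. This is the plan's one additional patient.

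**Step 2. Literal reading, P<0.05 at both looks.** Under the null hypothesis the two statistics are bivariate normal with correlation √(22/N). The error is P(|Z₁|>1.96 or |Z₂|>1.96).

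| Final N | t = 22/N | Type I error |
|---|---|---|
| 28 | 0.786 | 7.16% |
| 29 | 0.759 | 7.30% |
| 42 | 0.524 | 8.23% |

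The row for 42 shows what a larger N under option 3 could do. It treats that N as fixed in advance. Simulating the three-treatment repeated-measures F test under sphericity at 22 and 29 gives 7.45% (4 million runs) and 7.48% (2 million runs).

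**Step 3. O'Brien-Fleming at 22 of 29.** Here c = 2.016 and z₁ = 2.016/√0.759 = 2.315. The two-sided levels are 0.0206 at the interim and 0.0438 at the end, for a total of 5.0%. Applied unchanged to the F test, these normal-scale levels give 5.13% to 5.16% in simulation, so they need recalculating for the test actually used.

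**Step 4. Mixed readings at N = 29 (normal scale).**

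| Interim level | Final level | Type I error |
|---|---|---|
| 0.05 | 0.05 | 7.3% |
| 0.05 | 0.0438 | 6.9% |
| 0.0206 | 0.05 | 5.6% |
| 0.0206 | 0.0438 | 5.0% |

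Even a team that applies the right interim boundary but keeps the final level of section 1.3 exceeds 5%.

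**Step 5. Which rule does the extra patient fit?** Take the plan's 80% at a fixed N of 28 as given, so the drift is 1.960 + 0.842 = 2.802 at 28 completers.

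| Rule | Power, N = 28 | Power, N = 29 |
|---|---|---|
| Single test at 0.05 | 80.0% | 81.4% |
| Two looks at 0.05 | 82.3% | – |
| O'Brien-Fleming | 79.2% | 80.6% |

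Two looks at 0.05 raise power and need no extra patient. Only stricter boundaries create the shortfall that one more patient makes up.

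**The case against.** The strongest reply is that section 1.4 does name O'Brien-Fleming, and that method is a pair of boundaries. Its sample size inflation means nothing without them, and steps 1 and 5 show that the boundaries reproduce the extra patient. On this view the error is 5%, the sentence in section 1.3 was never meant for the interim, and the SAP lacks only a number. The reading is plausible and probably reflects the intention. It does not settle the matter: the stopping option does not refer to the method, the only defined level is 0.05, and nothing lowers the final level.

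Other points on that side have some weight:

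- **Option 1 is permissive.** Recruitment may stop but need not. The 7.3–7.5% assumes that a significant interim result is always claimed as positive, whether or not recruitment stops.
- **The final N of 29 is inferred.** The SAP does not say whether the extra patient is added to the 28 completers or to the 42 recruits. At N = 28 the levels would be 0.0227 and 0.0434. The digits change, but the point does not.
- **Option 3 re-estimates N from the accumulated data.** The 5% figure strictly needs a prespecified N. For illustration, suppose N is re-estimated from the observed interim effect with a minimum of 29. Keeping the final level at 0.0438 then gives 5.6% with a cap of 42 and 6.1% with a cap of 60. Recalculating the final level brings these to 5.1% and 5.3%. A small excess can therefore remain after the fix.
- **Section 1.3 cites a trial design section that is not shown.** Boundaries could be given there. But this SAP itself sets the interim rule and the significance level, so the levels belong here.

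**Conclusion.** The concern holds. The SAP gives a stopping rule and a significance level which, followed as written, do not control type I error at 5%. The error is about 7.3% for a single contrast and 7.5% for the F test, with looks at 22 and 29. It would be 8.2% on the normal scale if the final N were 42. Under O'Brien-Fleming at both looks it is 5.0% on the normal scale. The finding is not that error is certainly inflated, but that the text leaves the threshold open for any interim P between about 0.021 and 0.05. These figures assume two-sided testing and a final N of 29, and the power figures take the plan's 80% at 28 as given. The type I error figures do not depend on how 28 was derived. This must be fixed before the interim data are seen.

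**What to change.** 1. In section 1.4, option 1, replace the condition with: *the O'Brien-Fleming boundary is crossed for the treatment test on the primary sodium endpoint (about P ≤ 0.021 at 22 of 29 completers).*
2. In section 1.3, add: *the final test of that endpoint uses the matching O'Brien-Fleming level (about P ≤ 0.044) in place of 0.05.*
3. State that both levels are on the normal scale and will be recalculated for the actual information fraction and the test used. This includes the case where option 3 changes the final N.

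Alternatively, remove the efficacy stop and keep 0.05 for a single final test.

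The cost is SAP wording only. Both thresholds become stricter than 0.05. The extra patient already planned covers the loss: power at N = 29 is 80.6% with the boundaries, against 81.4% for a single test at 0.05.

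### Option 3 of the interim analysis redoes the power calculation after a non-significant open-label look without fixing the target, a maximum N or the final level, so type I error can rise if N is extended

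*SAP*

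**What the plan says.** Section 1.4 of the SAP states: "An interim analysis is planned after recruiting and completing the follow up of 22 patients". Three outcomes follow.

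- Option 1: on significance, recruitment may stop.
- Option 2: a non-significant study judged futile, or one with severe side effects, stops at once. No futility criterion is given.
- Option 3: for a non-significant result, "an additional power analysis calculation will be reassessed based on the realistic 1st endpoint data accumulated".

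O'Brien-Fleming is named only to support the closing statement that "it is estimated that one additional patient should be recruited to keep the study powered". No boundary values are printed.

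Three other places bear on this:

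- Section 1.1 sets the planning assumption: "The cutoff effect size was defined as the difference of 20 mmol in urine sodium measurement with an SD of 19". It does not say which SD the 19 is.
- Section 1.2 allows for 70% retention: "we aim to recruit 42 patients in total". This is a recruitment target, not a limit on re-estimation.
- Section 1.3 gives the only significance level, "A value of $P < 0.05$ will be considered significant", without dividing it between looks. It also shows that the effect is visible at the interim: "The treatments will be administered in a cross-over open-label trial".

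**The concern.** Option 3 comes into play after an efficacy test has been done and seen, in an open-label trial, and it draws on the accumulated primary-endpoint data. Its wording lets the observed effect replace 20 mmol. It also leaves the size of any extension and the final test level open.

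Two things can then push type I error above 5%:

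- A final level set for looks at 22 and 29 is too lenient for a larger final N, even if that N is chosen without looking at the data. The two looks are then less correlated.
- Choosing N from the observed effect adds a further, smaller amount.

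A rule settled only after the look cannot be shown to be independent of the result.

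**Working it through.** **Inputs.** From the SAP: N = 28, power 80%, 20 mmol, SD 19 (1.1); retention 70%, 42 recruited (1.2); level 0.05 (1.3); interim at 22, one extra patient under O'Brien-Fleming (1.4). Assumed: two-sided testing; a three-treatment repeated-measures F test with sphericity and no period or carryover terms, as a stand-in for the mixed model of 1.3; caps on evaluable N of 35, 42, 60 and 84. At 70% retention the caps mean recruiting 35/0.7 = 50, 42/0.7 = 60, 60/0.7 = 86 (rounded up) and 84/0.7 = 120. The cap of 42 evaluable is not the 42 recruited in 1.2.

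**Step 1: the plan's own figure.** For two looks at fraction 22/28, total error 0.05 and 80% power, the inflation factor is 1.020 (classical O'Brien-Fleming) or 1.030 (spending type). 28 x 1.020 = 28.6 and 28 x 1.030 = 28.8; both round up to 29. The one-patient allowance is reproduced, and 29/0.7 = 41.4 rounds up to the 42 of 1.2. It presumes a final N fixed in advance.

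**Step 2: levels for 22/29.** Spending type: 0.0244 interim, 0.0414 final. Classical: 0.0206 and 0.0438.

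**Step 3: null simulation.** With F the interim statistic, f² = 2F/22. The effect-driven rule is N = 10/f², rounded up and held between 29 and the cap. The final test pools all patients at the unchanged 0.0414. There were 4 million trials per setting (1 million for the stop rule). Without extension the error is 5.1%.

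| Cap (evaluable) | N fixed at cap, 0.0414 kept | N from observed effect, 0.0414 kept | N from observed effect, always stop if required N exceeds cap |
|---|---|---|---|
| 35 | 5.5% | 5.6% | 3.3% |
| 42 | 5.7% | 6.0% | 3.8% |
| 60 | 6.0% | 6.6% | 4.6% |
| 84 | 6.1% | 7.0% | 5.2% |

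Against 5.1%, the unchanged level adds about 0.4, 0.6, 0.9 and 1.0 points, and use of the observed effect adds a further 0.1, 0.3, 0.6 and 0.9. Classical levels give the same effect-driven totals within 0.1 point.

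**Step 4: what restores control.** Solving the final level for the new N while still choosing N from the observed effect gives 5.3%, 5.4%, 5.8% and 6.0%, so the level alone is not enough at large caps. Re-estimating only the SD and also solving the level gives 5.1-5.3% (caps 42 and 60).

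**Step 5: a separate matter.** P < 0.05 at both looks gives 7.5% with no extension, and 8.0-9.6% with an effect-driven one.

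**Step 6: the SD scale.** Noncentrality is n x (sum of squared deviations of the means)/variance. For assumed means 0, 0, 20 that sum is 6.67² + 6.67² + 13.33² = 266.7. With residual variance 19² = 361, 15 patients give 81.3% power. With 2 x 361 = 722 (SD 19 x √2 = 26.9), 27 patients give 79.0% and 28 give 80.6%. Scaling N on the wrong SD would change it by a factor of about 2.

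**The case against.** - **The rise is conditional.** A reader might infer that option 3 necessarily inflates type I error. The SAP does not support that. It says only that the power calculation will be revisited, not that N will change, that the observed effect will replace 20 mmol, or that the final level will stay put. An SD-only update with a solved final level is nearly harmless. This objection stands: the claim is that error can rise.
- **Option 2 could absorb much of the rise.** Under the null, the effect-driven N exceeds the cap in about 95%, 92%, 83% and 72% of trials (caps 35, 42, 60, 84). A futility judgement would most plausibly stop these trials, and the last column of the table shows the result. So 5.6-7.0% are upper figures. But option 2 has no criterion, so it cannot be counted on for error control.
- **The larger caps are far from the plan.** Caps of 60 and 84 mean recruiting 86 and 120 against 42. At caps of 35 and 42 the rise is 0.5-0.9 points. This stands, although the SAP rules out none of the caps.
- **P < 0.05 at both looks is another issue.** It concerns the missing interim level and arises without option 3, and naming O'Brien-Fleming makes that reading less natural. It is therefore kept apart.
- **The SD match is back-solved.** A reader might conclude that 28 is wrong. The SAP states neither the type of SD nor the pattern of means, so that does not follow.

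**Conclusion.** The point holds in conditional form. As written, option 3 allows an extension chosen from the observed effect after a seen, non-significant test, with no fixed target, no maximum N and no matching final level. The one-patient allowance does not cover that.

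If the 22/29 O'Brien-Fleming levels are kept, type I error can go from about 5.1% to 5.6-6.0% at assumed caps of 35-42 evaluable patients and to 6.6-7.0% at 60-84. This assumes that option 2 is never used for futility and that the simplified F test stands in for the mixed model. The size is modest, and the wording should be settled before the 22-patient look.

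The SD scale is a subsidiary gap: a re-estimated SD has nothing defined to be compared with until 1.1 says what the 19 is.

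**What to change.** Rewrite option 3 along these lines:

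> The 20 mmol target stays fixed. Only the SD is re-estimated, on the scale of the original calculation, which is [state]. N = 29 x (estimated SD / planning SD)², not below 29 and not above [maximum]. The interim level is fixed in advance for 22/29 under [named O'Brien-Fleming version] and is not changed afterwards. The final level is solved so that the total two-sided error is 0.05, given the interim level already used and the new N.

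| Version | Interim | Final, N = 29 | N = 42 | N = 60 |
|---|---|---|---|---|
| Spending | 0.0244 | 0.0414 | 0.0346 | 0.0314 |
| Classical | 0.0206 | 0.0438 | 0.0379 | 0.0349 |

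The clause on the interim level already used is essential. A fresh boundary drawn at 22/42 would give a looser final level of 0.0473 (spending) or 0.0476 (classical), which is not valid once 0.0244 or 0.0206 has been used at the interim.

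State in 1.1 which SD the 19 is before any scaling. A model-based residual SD or a treatment-blinded SD will do if prespecified. If the sponsor wants to use the observed effect, prespecify a combination or conditional-error test instead of the pooled test.

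**Cost.** This is SAP wording, with no new data items. N can no longer be tuned to the observed effect, and more patients may be needed if the SD is larger than planned. On the assumed variance of 722 and means 0, 0, 20, trials that continue average about 33 patients if the SD is as planned. If it is 30% higher, they average 41 (cap 42) or 50 (cap 60), and power rises from 57% at 29 patients to 72% or 80%. These patient and power figures hold only on that assumption.
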